7.5.2. Rescue Medications

Rescue medications are defined as medications taken to treat a migraine attack (in addition to the study drug) within 2 hours after taking the study drug. Rescue medications taken during the study will be reported in the eCRF as concomitant medications.

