7.5. MEDICATION

All medications including Concomitant medications, prohibited medications, and Rescue Medications will be classified using the Anatomical Therapeutic Chemical (ATC) classification and preferred drug names from the World Health Organization Drug Dictionary (WHO-DD), version March 2016.

Summaries of medications will be presented in tabular form using the highest level ATC term as an upper classification and the preferred drug name as a lower classification level. All medications will be summarized and sorted by descending counts in the upper classification term and the lower classification term within the upper. For each subject, the medication will be counted only once within the upper classification level and only once within the lower classification level.

Separate listings will be provided for concomitant, prohibited, and rescue medications taken during the study separately.

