8.1.2. The Proportion of Migraines and Subjects Experiencing Most Bothersome Other Symptom Freedom

The proportion of subjects with absence of the most bothersome (MBS) other symptom among nausea, photophobia, and phonophobia at 30 minutes, 2 hours, 12 hours, 24 hours, and 48 hours after dosing for the 1st, 5th, 15th, and 25th migraine a subject experiences will be summarized descriptively. In order to be MBS free, the subject must not have taken a rescue medication up until the specified time point.

The proportion of migraines that are MBS free without the use of rescue medication at 30 minutes, 2 hours, 12 hours, 24 hours, and 48 hours after dosing will be summarized descriptively.

The MBS is the symptom other than pain that is most bothersome most of the time with their migraine. (Sick to their stomach, sensitive to light, sensitive to sound/noise). Patients are asked to identify their most bothersome migraine-associated symptom in addition to pain at Visit 2.

A subject's MBS is obtained via the eDiary, and must be present pre-dose in order to be included in the analysis.

8.1.3. The Proportion of Migraines with Nausea Freedom, Photophobia Freedom, and Phonophobia Freedom

Regardless of the associated symptom identified as MBS, all three important migraine-associated symptoms (i.e., nausea/vomiting, photophobia, and

phonophobia) will be assessed separately. A binary scale (present or absent) will be used for associated symptoms. The proportion of migraines that are nausea-free, photophobia-free, and phonophobia-free without the use of rescue medication at 30 minutes, 2 hours, 12 hours, 24 hours, and 48 hours after dosing will be summarized descriptively. Both nausea and vomiting must be absent in order for the migraine to be considered nausea-free.

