8.1.5. The Proportion of Migraines Requiring Rescue Medication within 2 Hours Post-Dose

Rescue medications are defined as medications taken to treat a migraine attack (in addition to the study drug) within 2 hours after taking the study drug. Rescue medication data will be obtained from the eDiary. The proportion of migraines requiring rescue medication within 2 hours of initial treatment will be summarized descriptively.

8.1.6. The Proportions of Migraines with Sustained Pain Freedom from 2 to 24 Hours Post-Dose and from 2 to 48 Hours Post-Dose

The proportion of migraines that are “sustained pain-free”, defined as having no headache pain at 2 hours after dose, with no use of rescue medication, and no relapse of headache pain within 24 hours (24-hour sustained pain-free) post-dose will be summarized descriptively.

The proportion of migraines that are sustained pain-free from 2 to 48 hours will also be summarized descriptively.

8.1.7. The Proportion of Migraines with Migraine Recurrence within 24 and 48 Hours Post-Dose

Migraine recurrence between 2 to 24 hours (or 2 to 48 hours) is defined as pain-free at 2 hours post-dose, with pain (mild, moderate, or severe) reported within 24 hours (or 48 hours) post-dose or with rescue medication taken at any time 2 to 24 hours (or 48 hours).

The proportion of migraines that have recurred between 2 to 24 hours post-dose (and 2 to 48 hours post-dose) will be summarized.

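### The SAP's rescue-medication definition stops at 2 h, contradicting 8.1.7 and leaving the later rescue window unclear in 8.1.3, 8.1.4 and 8.1.6; migraine baseline is worded as the first-ever dose

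*SAP*

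**What the plan says.** SAP 7.5.2 defines rescue medication as "medications taken to treat a migraine attack (in addition to the study drug) within 2 hours after taking the study drug", and 8.1.5 repeats the definition. Neither document gives another. On data sources, 7.5.2 says "Rescue medications taken during the study will be reported in the eCRF as concomitant medications", while 8.1.5 says "Rescue medication data will be obtained from the eDiary".

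The efficacy sections then use the term as follows.

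- 8.1.1 (pain freedom) requires that no rescue be reported in the timeframe belonging to each time point: 30 min, 2, 12, 24 and 48 h.
- 8.1.2 (most bothersome symptom, MBS) says that to be MBS free "the subject must not have taken a rescue medication up until the specified time point". The migraine-level sentence after it reads "MBS free without the use of rescue medication at 30 minutes, 2 hours, 12 hours, 24 hours, and 48 hours after dosing".
- 8.1.3 (nausea, photophobia and phonophobia freedom) and 8.1.4 (pain relief) require no rescue at the same five time points, but do not say over what period rescue is looked for.
- 8.1.6 (sustained pain freedom) requires "no headache pain at 2 hours after dose, with no use of rescue medication, and no relapse of headache pain within 24 hours", and extends this to 48 h.
- 8.1.7 (recurrence) requires freedom from pain at 2 h, followed by reported pain "or with rescue medication taken at any time 2 to 24 hours (or 48 hours".

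On baseline, SAP 6.2.1 places the migraine and headache baseline at the eDiary time-0 entry before the first administration of product. It uses the same phrase for the other safety and baseline variables, where it means the first dose in the study. SAP 13 explains that most efficacy endpoints were moved from subject level to migraine level.

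**The concern.** A defined term normally carries its definition wherever it is used. If that is done here, medication taken after 2 h is never rescue. The rescue clause of 8.1.7 is then essentially empty, and the 12, 24 and 48 h conditions in 8.1.1 and 8.1.2 are cut back to the first 2 h. Where the endpoint text gives no clear window of its own (8.1.3, 8.1.4, 8.1.6), nothing in the SAP stops the 2-h limit from applying.

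Late medication is a realistic event. Protocol 3.2.5 bars aspirin, acetaminophen, NSAIDs and similar migraine medication only until 2 h after application. The definition therefore covers the period in which these drugs are barred and omits the period in which they are allowed.

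Two programmers could both follow the SAP and report different 12–48 h rates. In an open-label, single-arm study, that choice should not be left until results can be seen.

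The baseline wording raises a smaller, separate problem. Pain relief in 8.1.4 is defined relative to baseline, so a single baseline from the first treated attack would be the wrong comparator for every later attack.

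**Working it through.** The plan has no figure to reproduce. SAP 3.5 gives the sample size no statistical basis, and efficacy is summarised descriptively. The check is therefore of the text, followed by a count of cases.

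**1. Windows side by side.**

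| SAP section | Window in its own text | With the 7.5.2 definition inserted |
|---|---|---|
| 8.1.1 pain freedom | to each time point | 0–2 h, even at 12, 24, 48 h |
| 8.1.2 MBS freedom | to each time point | 0–2 h, even at 12, 24, 48 h |
| 8.1.3 nausea, photophobia, phonophobia | unclear | 0–2 h |
| 8.1.4 pain relief | not stated | 0–2 h |
| 8.1.6 sustained pain freedom | 24 or 48 h attached to relapse; unclear for rescue | 0–2 h |
| 8.1.7 recurrence | 2–24 or 2–48 h | nothing beyond 2 h itself |

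At 30 min and 2 h, everything taken before the assessment falls inside the 2-h limit, so both readings agree.

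**2. One attack traced through.** Take an attack with pain score 0 at 2, 12, 24 and 48 h.

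- Other migraine medication at 1 h: rescue on either reading. The attack is not pain-free from 2 h on and not sustained pain-free.
- Medication at 6 h, 2-h definition throughout: pain-free at 12, 24 and 48 h, sustained pain-free to 24 and 48 h, not recurred.
- Medication at 6 h, windows to the time point throughout: none of those successes, and recurred by 24 and 48 h.
- Medication at 6 h, definition in 8.1.6 but own text in 8.1.7: both sustained pain-free and recurred.
- Medication at 30 h: the same differences, but only for the 48 h results.

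In every case that differs, the 2-h definition is the more favourable to M207.

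**3. What the size would depend on.** Let P be the share of attacks pain-free at 24 h when only medication in 0–2 h disqualifies, and r the share of those with other migraine medication between 2 and 24 h. With the window run to 24 h the rate is P × (1 − r), so the overstatement is P × r. Neither value is in the documents. Assuming P = 50–80% and r = 5–30%, the difference runs from 0.50 × 0.05 = 2.5 points to 0.80 × 0.30 = 24 points.

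For sustained pain freedom, Protocol Table 4 gives 34/82 = 41.5% pain-free at 2 h on 3.8 mg in the earlier single-attack trial. If 5–20% of those attacks (assumed) are medicated later and show no pain, the overstatement is 41.46 × 0.05 = 2.1 to 41.46 × 0.20 = 8.3 points. These figures show how the rate moves; they are neither estimates nor bounds.

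**4. Baseline.** Under 8.1.4, relief means mild or no pain from a moderate or severe baseline, or no pain from a mild baseline. Pre-dose pain has three levels for attack 1 and three for the current attack, and post-dose pain has four: 3 × 3 × 4 = 36 combinations. Post-dose none is relief, and post-dose moderate or severe is not, whatever the baseline. Only post-dose mild can differ, and only when exactly one of the two baselines is mild: (1 × 2) + (2 × 1) = 4 combinations.

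- Attack 1 mild, current attack moderate or severe: real relief is lost (2 combinations).
- Attack 1 moderate or severe, current attack mild: unchanged mild pain is called relief (2 combinations).

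Mild attacks can qualify. Protocol 6.1.4 needs two of four characteristics, of which moderate or severe pain is only one, and the treatment diary in Appendix 3 offers mild as a pre-dose answer.

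**The case against.** The best reply is that the intent is fairly clear. The Protocol synopsis lists rescue use among the assessments made through 48 h. The eDiary item in Protocol Appendix 3 asks about other migraine medication since patch application, so each answer already covers dosing to that entry. The 2-h limit belongs to one endpoint (Protocol 7.1.2, SAP 4.1) and looks to have been carried into the general definition. Because the literal reading empties part of 8.1.7, a careful programmer would query it. The table shells are a separate document (SAP 20.1) and may state the windows, and Listing 16.2.6.2.4 will show all eDiary data. For baseline, the reference to time 0, the rule in 8.1.2 that the MBS be present pre-dose, and the migraine-level endpoints all suggest a per-attack baseline.

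Most of this stands as evidence of intent. It does not remove the contradiction between 7.5.2 and 8.1.7, and the SAP has no rule for deciding between the definition and the endpoint text.

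Some stronger readings fail. A reader might infer that migraine-level MBS freedom also lacks a window, but the sentence before it in 8.1.2 says what MBS free means and runs to the time point. A reader might infer that sustained pain freedom and recurrence will overlap. They do so only if opposite readings are used in adjacent sections.

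**Conclusion.** The point holds as a defect of definition. The 2-h limit contradicts 8.1.7, is narrower than 8.1.1 and 8.1.2 require at 12–48 h, and leaves five endpoints without an unambiguous rescue window: nausea, photophobia and phonophobia freedom, pain relief, and sustained pain freedom. If the defined term is applied, late success is overstated and recurrence understated, both in favour of M207.

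The amount cannot be found from the documents. It would be wrong to infer that the late rates will be inflated by any particular figure, since the illustration rests on assumed rates of late medication.

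The baseline wording is a lesser defect. It touches pain relief at any time point, including 30 min and 2 h, but only when post-dose pain is mild and exactly one of the two baselines was mild. The errors run both ways, so a bias in one direction should not be inferred.

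Efficacy is secondary and descriptive, no test or power is involved, and the primary safety objective is unaffected. The correction is worth making before database lock because it is cheap and removes a discretionary choice.

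**What to change.** Amend the SAP as follows.

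- **7.5.2:** define rescue as any medication other than M207 taken for the treated migraine from dosing through 48 h. Keep 2 h only as the window of endpoint 8.1.5.
- **8.1.1–8.1.4 and 8.1.6:** count rescue if the eDiary item on other medication since application is answered Yes at any entry up to and including the assessed time point (24 or 48 h for 8.1.6).
- **8.1.7:** require freedom from pain at 2 h with no rescue reported through the 2-h entry, then count rescue first reported after that entry and up to 24 or 48 h. Without this lower bound, medication at 1 h would count as recurrence.
- **6.2.1:** for attack-level endpoints, baseline is the eDiary time-0 entry of the same treated attack.

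The cost is two definitions and the window wording. No new data are needed: the eDiary asks about other medication at every post-dose entry and records pre-dose severity for each attack. These are analysis definitions only and do not change what subjects may take. The downside is that late efficacy rates may be slightly less favourable.

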8. EFFICACY

All efficacy analyses will be based on the mITT Population.

8.1. EFFICACY ENDPOINTS AND ANALYSIS

The following efficacy endpoints will be summarized using descriptive statistics:

8.1.1. The Proportion of Migraines and Subjects Experiencing Pain Freedom

The proportion of subjects who are pain-free without the use of rescue medication (i.e., a pain severity score of 0 and no rescue medication reported within the given timeframe) at 30 minutes, 2 hours, 12 hours, 24 hours, and 48 hours after dosing for the 1st, 5th, 15th, and 25th migraine a subject experiences will be summarized descriptively;

The proportion of migraines that are pain-free without the use of rescue medication (i.e., a pain severity score of 0 and no rescue medication reported within the given timeframe) at 30 minutes, 2 hours, 12 hours, 24 hours, and 48 hours after dosing will be summarized descriptively.

8.1.2. The Proportion of Migraines and Subjects Experiencing Most Bothersome Other Symptom Freedom

The proportion of subjects with absence of the most bothersome (MBS) other symptom among nausea, photophobia, and phonophobia at 30 minutes, 2 hours, 12 hours, 24 hours, and 48 hours after dosing for the 1st, 5th, 15th, and 25th migraine a subject experiences will be summarized descriptively. In order to be MBS free, the subject must not have taken a rescue medication up until the specified time point.

The proportion of migraines that are MBS free without the use of rescue medication at 30 minutes, 2 hours, 12 hours, 24 hours, and 48 hours after dosing will be summarized descriptively.

The MBS is the symptom other than pain that is most bothersome most of the time with their migraine. (Sick to their stomach, sensitive to light, sensitive to sound/noise). Patients are asked to identify their most bothersome migraine-associated symptom in addition to pain at Visit 2.

A subject's MBS is obtained via the eDiary, and must be present pre-dose in order to be included in the analysis.

8.1.3. The Proportion of Migraines with Nausea Freedom, Photophobia Freedom, and Phonophobia Freedom

Regardless of the associated symptom identified as MBS, all three important migraine-associated symptoms (i.e., nausea/vomiting, photophobia, and

phonophobia) will be assessed separately. A binary scale (present or absent) will be used for associated symptoms. The proportion of migraines that are nausea-free, photophobia-free, and phonophobia-free without the use of rescue medication at 30 minutes, 2 hours, 12 hours, 24 hours, and 48 hours after dosing will be summarized descriptively. Both nausea and vomiting must be absent in order for the migraine to be considered nausea-free.

8.1.4. The Proportion of Migraines with Pain-Relief

In addition to all above, the proportion of migraines with pain relief without rescue medication use (improvement of pain severity to mild or none from moderate or severe at baseline, or to none from mild at baseline) at 30 minutes, 2 hours, 12 hours, 24 hours, and 48 hours after dosing will also be summarized descriptively.

8.1.5. The Proportion of Migraines Requiring Rescue Medication within 2 Hours Post-Dose

Rescue medications are defined as medications taken to treat a migraine attack (in addition to the study drug) within 2 hours after taking the study drug. Rescue medication data will be obtained from the eDiary. The proportion of migraines requiring rescue medication within 2 hours of initial treatment will be summarized descriptively.

8.1.6. The Proportions of Migraines with Sustained Pain Freedom from 2 to 24 Hours Post-Dose and from 2 to 48 Hours Post-Dose

The proportion of migraines that are “sustained pain-free”, defined as having no headache pain at 2 hours after dose, with no use of rescue medication, and no relapse of headache pain within 24 hours (24-hour sustained pain-free) post-dose will be summarized descriptively.

The proportion of migraines that are sustained pain-free from 2 to 48 hours will also be summarized descriptively.

8.1.7. The Proportion of Migraines with Migraine Recurrence within 24 and 48 Hours Post-Dose

Migraine recurrence between 2 to 24 hours (or 2 to 48 hours) is defined as pain-free at 2 hours post-dose, with pain (mild, moderate, or severe) reported within 24 hours (or 48 hours) post-dose or with rescue medication taken at any time 2 to 24 hours (or 48 hours).

The proportion of migraines that have recurred between 2 to 24 hours post-dose (and 2 to 48 hours post-dose) will be summarized.

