3.2.5 Prior and Concomitant Medications Allowed During the Study

Medications that are considered necessary for the subject's welfare and are not specifically prohibited ([Section 6.2.11](#)), may be given at the discretion of the investigator. All medication(s) taken within 30 days prior to the screening visit and throughout the study must be recorded in the appropriate source document and in the case report form (CRF). Over the counter medications, topical skin ointments and/or creams, prescription medications, herbal supplements and/or vitamins will be recorded as concomitant medications.

Migraine prophylaxis medications are allowed if subjects have been on a stable dose for at least 30 days prior to screening and with no changes during the study.

Medications with ergot or another triptan or vasoconstrictor drugs are prohibited on the day of a confirmed migraine prior to M207 application and for 24-hours post-administration of M207.

Aspirin, acetaminophen, NSAIDS and other PRN or daily medications indicated specifically for migraine symptoms are prohibited on the day of a confirmed migraine prior to M207 application and during the two hours following M207 application.

Following M207 application, subjects will enter into the eDiary whether they took any medications (other than M207) for migraine symptoms prior to M207 application (on the day of application) or during the 48 hours post M207 application.

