6.2.11 Concomitant and Prohibited Medications

Concomitant medications, taken within 30 days of screening and throughout the study, include over the counter medications, topical skin ointments and/or creams, prescription medications, herbal supplements, and/or vitamins. These medications will be recorded on the appropriate source document and on the appropriate CRF at all visits including screening, run-in, and end of study (or early discontinuation) through the duration of the study.

Migraine prophylaxis medications are allowed if subjects have been on a stable dose for at least 30 days prior to screening and with no changes during the study.

Medications with ergot or another Triptan or vasoconstrictor drugs are prohibited on the day of the confirmed migraine prior to M207 application and for 24-hours post-administration of M207.

Aspirin, acetaminophen, NSAIDS, and other PRN or daily medications taken specifically for migraine symptoms are prohibited on the day of a confirmed migraine prior to M207 application and during the two hours following patch application.

On the day of M207 application, subjects will enter into the eDiary whether they took any medications (other than M207) for migraine symptoms prior to M207 application and/or during the 48 hours post M207 application.

Table 12 lists all prohibited concomitant medications taken within 10 days prior to the Run-in Period and for the duration of this study.

Table 12: Prohibited Concomitant Medications

Drug Type	Medication
Monoamine oxidase inhibitors	Selegiline Tranlycypromine Isocarboxazid phenelzine
Selective serotonin reuptake inhibitors (SSRIs)	Paroxetine Fluoxetine Sertraline Citalopram Escitalopram Fluvoxamine
Serotonin-norepinephrine reuptake inhibitors (SNRIs)	Duloxetine Venlafaxine Desvenlafaxine Milnacipran Levomilnacipran
All Prescription Anticoagulants	Pradaxa Coumadin Eliquis Xarelto

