7.1.2 Efficacy Endpoints

- Proportion of subjects with pain freedom at 30 minutes, 2 hours, 12 hours, 24 hours, and 48 hour post-dose
- Proportion of subjects with most bothersome other symptom freedom at 30 minutes, 2 hours, 12 hours, 24 hours, and 48 hours post-dose

- Proportion of subjects with pain relief at 30 minutes, 2 hours, 12 hours, 24 hours and 48 hours post-dose
- Proportion of subjects with nausea freedom at 30 minutes, 2 hours, 12 hours, 24 hours and 48 hours post-dose
- Proportion of subjects with photophobia freedom at 30 minutes, 2 hours, 12 hours, 24 hours and 48 hours post-dose
- Proportion of subjects with phonophobia freedom at 30 minutes, 2 hours, 12 hours, 24 hours and 48 hours post-dose
- Proportions of subjects using rescue medication within 2 hours post-dose
- Proportion of subjects with migraine recurrence at 24 and 48 hours post-dose
- Proportion of subjects with sustained pain freedom from 2 to 24 hours post-dose and from 2 to 48 hours post-dose
- Frequency of responses on the migraine ACT

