 - The following text shows - **DO NOT APPLY THE PATCHES. YOU **HAVE NOT** REPORTED a qualifying migraine. Please save your answers and return to the diary next time you think you are experiencing a migraine attack.**
- *If a qualifying migraine:*
 - The following text shows - You have reported a qualifying Migraine. Please apply the patches now. **After applying the patches**, press next to answer the remaining questions.
- Where were the study drug patches applied? (Both to left arm, Both to right arm, Other)
 - If Other is checked for above question – the following text shows - You have applied the patches incorrectly. Both patches must be applied. What was the

reason for not applying both? (Applied one patch to left arm, Applied one patch to right arm, Technical problem with applicator and/or patch, None were applied)

Questions at the 30-minute diary post patch application

Please remove the patches from your upper arm, fold in half, and discard

- How bad is your headache pain? (None, Mild, Moderate, Severe)
- Are you nauseated (sick to your stomach)? (Yes, No)
- Did you vomit (throw up)? (Yes, No)
- Does light bother you? (Yes, No)
- Does sound or noise bother you? (Yes, No)
- Since applying the patches, did you take any medication to treat your migraine other than the patches you applied?
- After removing the patches, how much redness do you see on the skin? (None, Mild redness, Moderate colored redness, Beet colored redness)
- After removing the patches, how much swelling do you see? (None, Slight swelling, Moderate swelling, Severe swelling)
- After removing the patches, how much bruising of the skin do you see? (None, Less than a quarter of the application site has bruising spots, About one-half of the application site has bruising spots, More than one-half of the application site has bruising spots)
- After removing the patches, how much bleeding do you see? (None, pink color on skin, visible blood drop, active bleeding)

Post patch application: 2, 12, 24, 48 hours post patch application

- How bad is your headache pain? (None, Mild, Moderate, Severe)
- Are you nauseated (sick to your stomach)? (Yes, No)
- Did you vomit (throw up)? (Yes, No)
- Does light bother you? (Yes, No)
- Does sound or noise bother you? (Yes, No)
- Since applying the patches, did you take any medication to treat your migraine other than the patches you applied? (Yes, No)

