4. ENDPOINTS

4.1. EFFICACY ENDPOINTS

- Proportion of Migraines that are pain free at 30 minutes, 2 hours, 12 hours, 24 hours, and 48 hours post-dose
- Proportion of subjects with pain freedom at 30 minutes, 2 hours, 12 hours, 24 hours, and 48 hours post-dose for the 1st, 5th, 15th, and 25th migraine a subject experiences
- Proportion of migraines with most bothersome other symptom freedom at 30 minutes, 2 hours, 12 hours, 24 hours, and 48 hours post-dose
- Proportion of subjects with most bothersome other symptom freedom at 30 minutes, 2 hours, 12 hours, 24 hours, and 48 hours post-dose for the 1st, 5th, 15th, and 25th migraine a subject experiences
- Proportion of migraines with pain relief at 30 minutes, 2 hours, 12 hours, 24 hours and 48 hours post-dose
- Proportion of migraines with nausea freedom at 30 minutes, 2 hours, 12 hours, 24 hours and 48 hours post-dose
- Proportion of migraines with photophobia freedom at 30 minutes, 2 hours, 12 hours, 24 hours and 48 hours post-dose
- Proportion of migraines with phonophobia freedom at 30 minutes, 2 hours, 12 hours, 24 hours and 48 hours post-dose
- Proportions of migraines that require rescue medication within 2 hours post-dose
- Proportion of migraines that recurred within 24 and 48 hours post-dose
- Proportion of migraines with sustained pain freedom from 2 to 24 hours post-dose and from 2 to 48 hours post-dose
- Frequency of responses on the migraine assessment of current therapy (ACT)

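### The only rescue-medication endpoint covers the two hours in which other migraine medication is prohibited, and rescue after 2 hours is collected but never summarised as a per-attack rate

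*SAP*

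**What the plan says.** **Endpoint.** Protocol 7.1.2 lists "Proportions of subjects using rescue medication within 2 hours post-dose". SAP 4.1 changes the unit from subject to attack but keeps the window: "Proportions of migraines that require rescue medication within 2 hours post-dose". SAP 8.1.5 gives the analysis: "The proportion of migraines requiring rescue medication within 2 hours of initial treatment will be summarized descriptively". The table index (SAP 17) has one rescue table, 14.2.1.5, limited to 2 hours.

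**Definition.** SAP 7.5.2, repeated in 8.1.5, defines rescue medications as "medications taken to treat a migraine attack (in addition to the study drug) within 2 hours after taking the study drug".

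**Restrictions.** Under Protocol 3.2.5, aspirin, acetaminophen, NSAIDs and other migraine-specific medicines "are prohibited on the day of a confirmed migraine prior to M207 application and during the two hours following M207 application". Section 6.2.11 sets the same window. It makes ergots, other triptans and vasoconstrictors "prohibited on the day of the confirmed migraine prior to M207 application and for 24-hours post-administration of M207". SAP 7.5.1 repeats both rules.

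**Collection.** The protocol synopsis places rescue use among the efficacy assessments made out to 48 hours, and 3.2.5 has subjects record other migraine medication over the same 48 hours. Appendix 3 asks at 2, 12, 24 and 48 hours: "Since applying the patches, did you take any medication to treat your migraine other than the patches you applied? (Yes, No". The same question is asked at 30 minutes.

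**The concern.** A rescue rate is normally read as the share of attacks in which the study drug was not enough. That reading needs a window in which subjects are free to take something else. Here the window closes when most other medication first becomes allowed.

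Later use matters in this design. Protocol 3.1 gives one dose per attack, and 6.1.4 bars treating another attack with M207 within 48 hours of an application. In an attack that M207 does not control, other medication is the remaining treatment, and most of it is first permitted after 2 hours.

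At stake is a result listed under the secondary (efficacy) objective. A very low rate of attacks requiring rescue could be taken as evidence of benefit when the protocol's own rules help to produce it. How often subjects went on to other treatment would have no summary of its own.

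**Working it through.** No sample-size, power or alpha figure bears on this point, and the plan gives no expected rescue rate to reproduce. The check compares time windows and then traces where later rescue goes.

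**1. Windows side by side (hours after application)**

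| Item | Window | Source |
|---|---|---|
| Rescue endpoint | 0-2 | Protocol 7.1.2; SAP 4.1, 8.1.5, Table 14.2.1.5 |
| Restriction: aspirin, acetaminophen, NSAIDs, other migraine-specific medication | 0-2 | Protocol 3.2.5, 6.2.11; SAP 7.5.1 |
| Restriction: ergots, other triptans, vasoconstrictors | 0-24 | same sections |
| eDiary collection | 0-48 | Protocol 3.2.5, 6.2.11, Appendix 3 |

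**2. Overlap.** The endpoint's 2 hours lie wholly inside each restricted window: 2/2 = 100%.

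**3. Coverage.** 2/48 = 4.2% of the collected period is summarised as a rescue rate, and 46/48 = 95.8% is not. The rescue question is put at five post-dose times (30 min and 2, 12, 24 and 48 h). Two fall in the endpoint window, and 5 - 2 = 3 feed no rescue rate.

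**4. What the 0-2 h rate responds to.** Let *w* be the proportion of attacks in which the subject would want other medication within 2 hours, and *b* the proportion of those in which it is taken despite the restriction. The observed rate is *w* × *b*. With full compliance *b* = 0, so the rate is 0 for every *w*. With no compliance *b* = 1, and the rate is *w*. The documents give neither quantity, so the rate can lie anywhere from 0 to *w*. A low value cannot separate a small *w* (the drug worked) from a small *b* (the rule was followed).

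**5. Where rescue after 2 hours appears**

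- *Composites at 12, 24 and 48 h* (pain freedom, MBS freedom, nausea, photophobia and phonophobia freedom, pain relief: SAP 8.1.1 to 8.1.4) and *sustained pain freedom* (8.1.6). Rescue turns a success into a failure. Failures from rescue and from residual symptoms are pooled, so a rescue rate cannot be recovered.
- *Recurrence* (8.1.7). Only attacks pain-free at 2 hours can qualify. Attacks still painful at 2 hours are outside it. SAP 17 indexes no recurrence table.
- *Concomitant medication* (7.5, 7.5.2, Table 14.1.1.7). Each subject is counted once per drug, not per attack or by time since dose.
- *Listings.* Listings 16.2.4.5 and 16.2.6.2.4 would carry the data. SAP 7.5 promises a separate rescue listing, but SAP 19 does not index one.

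**6. The definition.** SAP 7.5.2 and 8.1.5 restrict rescue to 2 hours, yet 8.1.7 uses rescue taken between 2 and 24 (or 48) hours. Read literally, medication at 3 hours is not rescue. The rescue part of recurrence would then be empty, and an attack treated at 3 hours could count as pain-free at 24 hours. The later entries in step 5 that depend on the word rescue therefore hold only if the 2-hour limit is ignored.

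**7. Can it be repaired from existing data?** Yes. The diary item is cumulative since application. An attack answered No at 30 minutes and 2 hours and Yes at 12 or 24 hours belongs to >2-24 h. Extending to the 48-hour answer gives >2-48 h, which includes the first interval.

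**The case against.** The strongest defence is that this is an uncontrolled, open-label study with a safety primary objective and descriptive efficacy only. No test or primary conclusion rests on this row, and the protocol chose the window. That stands and limits the weight of the point. It does not make the row interpretable.

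Three stronger readings are tempting, and the documents do not support them.

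- *A reader might infer that rescue after 2 hours is never reported.* It enters the 12-48 h composites and recurrence (if the definition is read without its 2-hour limit), the concomitant-medication table and the listings. What is missing is a per-attack rate of its own.
- *A reader might infer that the endpoint simply counts protocol violations.* Early rescue can also signal treatment failure, and Protocol 5.2 lists rescue use under efficacy. The diary answer is yes/no, with no drug name or time of intake, so it does not by itself prove a breach. Protocol 3.2.5 speaks of medicines indicated for migraine symptoms, while 6.2.11 speaks of medicines taken for them. Exclusion criterion 11 tolerates limited opioid or barbiturate use. A Yes for such a drug is not clearly a breach under 3.2.5.
- *A reader might size the gap from the earlier trial's 3.8 mg results* (41.5% pain-free and 80.5% with pain relief at 2 hours), giving 100 - 41.5 = 58.5% and 100 - 80.5 = 19.5%. These are not rescue rates. They come from a single-attack trial that counted relief from moderate or severe pain. Here a mild attack can qualify, and mild to none counts as relief.

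A further fair objection is that a cumulative rate by 24 or 48 hours would still mix in 0-2 h use, and under the present SAP definition would equal it. This is accepted: the fix must use intervals after 2 hours and must change the definition.

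**Conclusion.** The point holds in this form: the sole rescue endpoint lies wholly within the prohibited period, so compliance pushes it toward zero whatever the efficacy. Rescue in the remaining 46 of 48 collected hours has no per-attack summary. An exact 0% follows only under perfect compliance, which is an assumption. The size of the unsummarised rescue use cannot be estimated from the documents.

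The consequence is confined to a descriptive result under the secondary objective and does not touch the safety conclusions. It is still worth correcting, because the row invites a favourable reading that it cannot support. The definition conflict between SAP 7.5.2/8.1.5 and 8.1.7 is a linked defect. Correcting the definition alone would leave this endpoint at 2 hours, and widening the endpoint alone would have no effect under the present definition.

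**What to change.** 1. **SAP 7.5.2 and 8.1.5:** remove the 2-hour limit from the analysis definition of rescue medication and reconcile it with 8.1.7.
2. **SAP 4.1, 8.1.5 and Table 14.2.1.5:** report the proportion of treated migraines with rescue first reported in 0-2 h, >2-24 h and >2-48 h, from the cumulative eDiary item, overall and by pain status at 2 hours. State how an attack with a missing 2-hour answer is handled, since SAP 6.3 imputes nothing and such an attack may not be assignable to an interval.
3. **Table footnotes:** say that 0-2 h use falls in the period when such medication is prohibited. Say also that the >2-24 h figure may include drug classes restricted to 24 hours, because the diary item does not identify the drug.
4. **SAP 13:** declare the change alongside the endpoint changes already listed there.

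The cost is SAP wording and a few more table rows, with no new data collection. The reported rescue rate will be higher. No change to the rescue or restriction rules is proposed.
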